8.4. Secondary Endpoints

The secondary endpoints for this study include the following. For these endpoints, baseline is defined as the last assessment prior to the first dose of study drug.

Efficacy Endpoints:

- Subject-rated pain due to acute back spasm using an NRS (0-10 scale, from no pain to worst possible pain) on Day 4 “right now”.
- Subject rating of medication helpfulness (SRMH; 1-5 scale, from poor to excellent) on Days 4 and 14.
- Subject-rated NRS (0-10 scale) of pain due to acute back spasm on Days 1 to 14; average over the past 12 hours.
- Subject-rated NRS (0-10 scale) of pain due to acute back spasm on Days 1 to 14; average over the past hour.
- Subject-rated NRS (0-10 scale) of average pain due to acute back spasm on rest or movement, rated at the end of the day on Days 1 to 14.
- Time to relief of pain from baseline due to acute back spasm using subject-rated NRS (0-10 scale) on Days 1 to 14.

- Clinician’s Global Impression of Severity (CGI-S) (1–5 scale) at baseline (Day 1).
- Clinician’s Global Impression of Change (CGI-C) 1-7 scale from worse to marked improvement) on Days 4 and 14.
- Patient’s Global Impression of Severity (PGI-S) (1-5 scale) at baseline (Day 1).
- Patient’s Global Impression of Change (PGI-C) based on subject’s global assessment (1-7 scale, from worse to marked improvement) on Days 4 and 14.
- Functionality assessment: fingers to floor distance (FFD) is an index of mobility of the spinal cord and is measured as distance in cm when standing with the spinal cord flexed with complete extension of knee joint, on Days 4 and 14 compared to baseline (Day 1) (assessments should be conducted at the same time of day for all three time points).
- Disability assessment at baseline (Day 1), Day 4, and Day 14:
 - Oswestry Pain and Disability (ODI) questionnaire (10 questions with one answer each for pain intensity, personal care, lifting, walking, sitting, standing, sleeping, sex life [if applicable], social life, and traveling).
- Use of rescue medications (measured daily, assessed as number of rescue tablets administered by the subject via smartphone/use of trial application). Patients are instructed not to take rescue medications on the day of clinic visits on Day 4 and 14.
- Quality of sleep rated by subjects starting at baseline (Day 1) and on Days 2 to 14.
- Visual Analogue Scale (VAS) score for subject-reported sleepiness measured in the clinic on at Day 4.

Safety Endpoints

- Clinical evaluations include:

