9.1. Inclusion Criteria

1. Ambulatory male or female, 18 to 65 years of age.
2. Current acute back pain and/or stiffness due to acute and painful muscle spasm starting within 7 days prior to study entry and more than 8 weeks after the last episode of acute back pain.
3. Subjects must have pain of 4 or more on the subject “right now” rating of pain intensity NRS scale of 0 – 10 points at baseline.
4. Must be willing to discontinue all medication used for the treatment of pain or muscle spasm on study entry at Day 1 including but not restricted to:
 - a. Ibuprofen (Motrin)
 - b. Diclofenac (Voltaren)
 - c. Celocoxib (Celebrex)
 - d. Naproxen (Aleve)
 - e. Tolmetin (Tolectin)
 - f. Cyclobenzaprine (Flexeril)
 - g. Cyclobenzaprine (Amrix)
 - h. Metaxolone (Skelaxin)
 - i. Methocarbamol (Robaxin)
 - j. Other nonsteroidal anti-inflammatory drugs (NSAIDs; e.g., aspirin)
 - k. Carisoprodol (Soma)
 - l. Tizanidine (Zanaflex, Sirdalud)
5. Pain localized below the neck and above the inferior gluteal folds.
6. Body mass index ranging between 18 and 35 kg/m².
7. All subjects must be capable of understanding and complying with the protocol and have signed the informed consent document.
8. Female subjects must have a negative urine pregnancy test at screening, must be postmenopausal (amenorrhea for at least 2 years), surgically sterile, or practicing or agree to practice an effective method of birth control if they are sexually active before study entry, during the study and for 2 weeks after the end of the study by using an acceptable method of contraception. Acceptable methods of birth control must be used for at least 14 days prior to the use of study drug. Acceptable methods of birth control include oral, injectable, subdermal implant, vaginal or patch contraceptives, intrauterine device (IUD; copper or hormonal IUD), or double-barrier method (e.g., condom, diaphragm or cervical cap with spermicidal foam, cream, gel, or suppository).
9. Subjects must be willing and able to comply with scheduled visits, treatment plan, laboratory tests, and other study procedures.

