6.4.1.2 Secondary Efficacy Variables

Secondary efficacy endpoints include assessments administered on a study-provisioned tablet at the clinical site on Day 1 (baseline), Day 4, and Day 14 or captured by the subject with smartphone/trial application daily at home from Day 1 to Day 14 (See Table 2)

- Subject-rated pain due to acute back spasm “right now” using NRS on Day 4
- Subject-rated average pain due to acute back spasm over past 12 hours using NRS on Days 1 to 14, measured in morning and evening.
- Subject-rated average pain due to acute back spasm over past 1 hour using NRS on Days 1 to 14, measured in morning and evening
- Subject-rated average pain at rest due to acute back spasm using NRS on Days 1 to 14, measured in evening
- Subject-rated average pain on movement due to acute back spasm using NRS on Days 1 to 14, measured in evening
- Subject rating of medication helpfulness (SRMH) using a scale of 1-5 on Days 4 and 14, where 1=poor, 2=fair, 3=good, 4=very good, and 5=excellent.
- Time to relief of pain due to acute back spasm (days) from baseline using subject-rated NRS of pain over past 12 hours. The first NRS score of 2 or lower will be used to define relief.
- Clinician’s Global Impression of Severity (CGI-S) using 1–5 scale at baseline (Day 1), where 1=no pain, 2=mild pain, 3=moderate pain, 4=severe pain, and 5=worst possible pain
- Clinician’s Global Impression of Change (CGI-C) using a scale of 1-7 on Days 4 and 14, where 1=Very Much Worse, 2=Much Worse, 3=Minimally Worse, 4=No Change, 5=Minimally Improved, 6=Much Improved, and 7=Very Much Improved

- Patient's Global Impression of Severity (PGI-S) using a scale of 1–5 scale at baseline (Day 1), where 1=no pain, 2=mild pain, 3=moderate pain, 4=severe pain, and 5=worst possible pain
- Patient's Global Impression of Change (PGI-C) based on subject's global assessment using a scale of 1-7 on Days 4 and 14, where 1=Very Much Worse, 2=Much Worse, 3=Minimally Worse, 4=No Change, 5=Minimally Improved, 6=Much Improved, and 7=Very Much Improved).
- Fingers to floor distance (FFD) measured at Baseline (Day 1), Day 4, and Day 14

FFD is an index of mobility of the spinal cord and is measured as distance in cm when standing with the spinal cord flexed with complete extension of knee joint, on Days 4 and 14 compared to baseline (Day 1) (assessments should be conducted at the same time of day for all three time points).

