SRMH values will be summarized categorically by treatment group for Days 4 and 14 for the ITT Population. The frequency and percentage of subjects in each response category will be presented. The comparison of each group to placebo will be conducted using a Wilcoxon Rank Sum test for the Day 14 values and p-values presented.

7.4.5.5 *Fingers to Floor Distance*

Fingers to floor distance will be assessed at Baseline, Day 4, and Day 14 and will be analyzed using a linear test of trend similar to the primary endpoint on Day 14. Pairwise estimates of the observed value will be presented.

7.4.5.6 *Global Symptom assessments (CGI and PGI)*

Global symptom assessments will be summarized by treatment group for the ITT population. CGI-S and PGI-S will be assessed at the baseline visit only. CGI-C and PGI-C will be assessed at Day 4 and Day 14. The frequency and percentage of subjects in each response category at Baseline, Day 4 and Day 14 will be presented. The comparison of each group to placebo will be conducted using a Wilcoxon Rank Sum test for the Day 14 values and p-values presented.

7.4.5.7 *Quality of Sleep*

Quality of sleep will be analyzed using the same methods described for the global symptom assessments in section 7.4.5.6. The comparison of each group to placebo will be conducted using a Wilcoxon Rank Sum test for the Day 14 observed values.

7.4.5.8 *Time to Pain Relief*

Time to pain relief (days) will be assessed using the NRS assessment of subject rating of pain over the past 12 hours. NRS assessments on or after Day 2 will be considered for time to relief. The first post-baseline occurrence of an AM or PM 12-hour NRS score equal to 2 or lower (0 = no pain, 10 = worst possible pain) will be used as the criterion for relief.

Subjects who withdraw from the study prior to the end of treatment visit or who complete the treatment period without having met the criteria for relief will be censored at the time of their last NRS assessment. Time to relief will be presented in days as (date of relief/censoring – date of first dose + 1).

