The number of subjects with relief and those censored will be summarized by treatment group for the ITT population. Estimates of the median times will be presented along with their associated 95% confidence intervals. Treatment group comparisons will be summarized with hazard ratios and their associated 95% CI from a Cox Proportional Hazards regression model with treatment as the main effect and p-values from a generalized Wilcoxon test.

The Kaplan Meier plots of time to pain relief by treatment group will be presented and display the subjects with relief and those censored at each study day.

A by subject listing of derived time to relief estimates will also be presented.

7.4.5.9 *Rescue Medication Use*

The use of study provisioned medication will be summarized using frequency counts and percentages for the number of tablets consumed by treatment group for the ITT population. Descriptive statistics will also be presented by treatment group. The number of days of medication use, average daily use (caplets/day of medication use) and total use will be tabulated using descriptive statistics. The frequency and percentage of subjects with rescue medication entry will be presented.

The Shapiro-Wilk test will be used to examine the assumption of normality for total rescue medication use across all dose groups. If this test is statistically significant (i.e., $p \leq 0.05$) then the assumption of normality is violated and the total rescue medication consumption will be analyzed using a Wilcoxon Rank Sum test.

However, if the assumption of normality holds (i.e., Shapiro-Wilk p-value > 0.05), then the total rescue medication consumption will be analyzed using an analysis of variance (ANOVA) model with randomized treatment as the main effect. The LSM and LSMD will be presented with associated 95% CI and p-values comparing each treatment group to placebo.

A data listing of rescue medication use will be presented and include the average number of tablets consumed and total number of tablets rescue medication consumed for each subject.

7.4.5.10 *Oswestry Disability Index*

ODI score (%) will be calculated as $(\text{total score} \times 2) / (\text{number of sections answered} / 10)$, rounded to the nearest integer, where the total score is the sum of the individual section scores.

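### The time-to-relief analysis leaves out baseline pain: the comparison is valid but probably gives up some power, and stratifying by the Day 1 score is a nearly free improvement

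*SAP*

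**What the plan says.** - **Event.** SAP 6.4.1.2 states: "The first NRS score of 2 or lower will be used to define relief". SAP 7.4.5.8 takes "The first post-baseline occurrence of an AM or PM 12-hour NRS score equal to 2 or lower" as relief. It adds that "NRS assessments on or after Day 2 will be considered for time to relief". Subjects without relief are "censored at the time of their last NRS assessment".
- **Entry.** Protocol 9.1, criterion 3: "Subjects must have pain of 4 or more on the subject" 'right now' rating at baseline. There is no upper limit, so entry scores run from 4 to 10.
- **Analysis.** SAP 7.4.5.8 takes hazard ratios from a "Cox Proportional Hazards regression model with treatment as the main effect and p-values from a generalized Wilcoxon test". No covariate or stratum is named. Protocol 17.4.2.2 names the same two methods.
- **Baseline adjustment elsewhere.** SAP 7.4.4 puts baseline NRS in the primary MMRM. SAP 7.4.6.1 extends this to secondary MMRMs that have a baseline value. SAP 7.4.5.10 adjusts ODI for its baseline. Time to relief is not covered by any of these.
- **Randomisation.** SAP 6.3.2 stratifies by site, not by starting pain.

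**The concern.** With a fixed target of 2, the nominal fall required is 4 - 2 = 2 points for a subject entering at 4 and 10 - 2 = 8 points for one entering at 10. Starting pain is therefore a likely predictor of when, and whether, the event occurs. The plan collects it from every eligible subject and uses it in its main models, but not here.

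When a prognostic factor is left out of a Cox model, the treatment hazard ratio averages over subjects with different underlying hazards. It moves toward 1, and the test loses sensitivity. At stake is efficiency on a secondary endpoint that bears on the onset-of-action objective (SAP 5.2).

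**Working it through.** **The plan's own figure.** For 80 per group, difference 0.9 and SD 2.0, two-sided 5% (SAP 7.6): 0.9 / (2.0 × √(2/80)) = 0.9 / 0.316 = 2.846, and power = Φ(2.846 - 1.960) = Φ(0.886) = 81%. This matches the 81% in Protocol Table 1. Neither document gives power, an event rate or a hazard ratio for time to relief.

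**Inputs from the documents.** 80 vs 80; entry score 4-10; Day 14 difference 0.9 and SD 2.0; two 12-hour ratings a day on Days 2-14; event at the first score of 2 or lower; time in days.

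**Inputs assumed, because the documents give none.** Baseline mean 6.8; baseline SD 1.2 or 1.6 before truncation to 4-10; comparator Day 14 mean 2.5 or 3.5; exponential improvement; no dropout. The nominal correlation of baseline with Day 14 pain is slope × baseline SD / 2.0, for example 0.5 × 1.6 / 2.0 = 0.40.

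**Tests.** The stratified Wilcoxon is Z = ΣU / √ΣV, summed over strata 4-5, 6-7 and 8-10. Within a stratum, U = Σ n(d₁ - d·n₁/n) over event days. Here n and n₁ are the numbers at risk in total and on active, and d and d₁ the corresponding events. The Cox columns compare treatment only with treatment plus a linear baseline term. There were 1,000 runs per scenario, so the Monte Carlo error is about √(0.7 × 0.3 / 1000) = 1.5 points.

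| Correlation | Wilcoxon power, unstratified → stratified | Change (points) | Cox power, treatment only → with baseline | Change (points) | Mean hazard ratio, treatment only → with baseline |
|---|---|---|---|---|---|
| 0 | 69-76% → 70-76% | -5 to +2 | 65-73% → 68-74% | 0 to 3 | 1.48-1.60 → 1.52-1.63 |
| 0.18-0.30 | 62-72% → 69-74% | -1 to +9 | 59-68% → 71-76% | 6 to 14 | 1.46-1.59 → 1.54-1.67 |
| 0.40 | 62-66% → 74-75% | +8 to +13 | 60-65% → 75% | 10 to 15 | 1.46-1.56 → 1.59-1.69 |
| 0.48 | 64-69% → 76-79% | +10 to +12 | 62-67% → 81-82% | 15 to 20 | 1.48-1.59 → 1.66-1.78 |
| 0.64 | 54-59% → 80% | +21 to +26 | 54-60% → 83-84% | 24 to 29 | 1.44-1.56 → 1.70-1.85 |

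With no treatment effect (correlations 0.40 and 0.64), all four methods rejected in 5-7% of runs.

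**Two further simulations of the Wilcoxon test.**
- Baseline mean about 6.5, SD 1.5, rating noise SD 1, 500 runs: 65-69% → 71-73% at correlation 0, 59-66% → 70-73% at 0.2, 56-63% → 70-75% at 0.4, and 48-56% → 77-82% at 0.6. Null rejection was 4.9% unstratified and 5.1% stratified.
- Difference 0.9, SD 2.0: 71% → 73% at correlation 0, 70% → 76% at 0.2, 66% → 79% at 0.4, and 61% → 83% at 0.6. Null rejection was 4-6%.

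**Sensitivity to the pain course.** This run used linear decline of 0.28 points a day unrelated to baseline, baseline mean 6.3, SD 1.5, an assumed effect of 0.05 points a day and 400 runs. Stratified Cox power rose from 35% to 55% (decline SD 0.10, noise 0.7), from 21% to 29% (0.15, 1.0) and from 16% to 17% (0.20, 1.5). The last two settings imply Day 14 SDs of 2.2-2.7, above the planned 2.0.

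**The case against.** The case for leaving the plan alone has several parts.

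- **Nothing is invalid.** Randomisation protects the unadjusted test, and the marginal hazard ratio is a legitimate estimand. This stands: the point is efficiency, not bias or inflated error.
- **Priority is low.** The endpoint is secondary, in a Phase 2 dose-ranging trial with no multiplicity control (SAP 7.4.6.5) and no power claim for it. Early effect is also tested by the baseline-adjusted Day 4 NRS (SAP 7.4.5.1), and no section names time to relief as the sole onset analysis. This stands and limits the weight of the point.
- **The baseline is not the same measure.** No pre-dose 12-hour rating is scheduled, so the 'right now' score must stand in. The daily 12-hour MMRM in SAP 7.4.5.2 lists no baseline covariate either. This is true, but a stratifying variable need only be prognostic and measured before dosing.

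Two stronger readings are tempting. First, a reader might infer that the fixed threshold departs from the protocol's "Time to relief of pain from baseline due to acute back spasm using subject-rated NRS (0-10 scale) on Days 1 to 14". The documents do not support that. The protocol sets no relief threshold, and 'from baseline' can mean the starting point of the clock. The SAP keeps that phrase, and the protocol synopsis omits it. Reaching 2 or lower is an acceptable definition, and stratifying would not change it: a fall from 10 to 3 would still not count.

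Second, a reader might infer that omitting baseline inflates the standard error. In the linear-decline runs, stratification slightly raised the mean standard error of the log hazard ratio (0.197 to 0.201, 0.191 to 0.194, 0.180 to 0.183). The gain comes from a hazard ratio further from 1.

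**Conclusion.** The point holds as a worthwhile, low-cost improvement. The plan leaves a probable predictor out of the one analysis where a fixed threshold makes it especially relevant, and gives no reason.

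Across the three simulations that varied the correlation, the Wilcoxon gain from stratifying is about zero (-5 to +6 points) at correlation 0, about -1 to +11 at 0.2-0.3, about 8-14 at 0.4, and above 20 only at 0.6 or more. A reader might conclude that the onset analysis loses much of its power. That would need a strong correlation, and the documents give no baseline SD, correlation or event rate from which to establish one. The figures also rest on the assumed pain course and on no dropout. A reader might also fear that a linear baseline term would distort type I error. The null runs do not show that: its rejection rate lay in the same 5-7% range as the other methods.

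**What to change.** In SAP 7.4.5.8, before unblinding, stratify the Cox model and the generalized Wilcoxon test by the Day 1 'right now' NRS, for example 4-5, 6-7 and 8-10. Report the stratified hazard ratios and p-values. Strata suit both procedures: the Wilcoxon test takes no covariate, and a stratified Cox model need not assume proportional hazards across baseline scores. Keep the relief definition and the Kaplan-Meier plots as planned. Because Protocol 17.4.2.2 specifies the treatment-only Cox model, record the change in SAP 7.7.1.

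The cost is one strata term in each procedure and no new data. The hazard ratio becomes conditional on baseline, and the text should say so. Power could fall by a few points if baseline pain turns out not to be prognostic.

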6.4.2.4.1 Vital Signs

Vital signs will include the measurement of supine and standing blood pressure, orthostatic assessments, heart rate, respiratory rate, and body temperature. Vital signs will be measured on Day 1 (Screening/Baseline visit) and on Days 4, 14, and 28. Weight and height will be measured at Screening/Baseline only.

6.4.2.4.2 12-Lead Electrocardiogram

Standard 12-lead ECGs will be administered at the clinic on Day 1 (Screening/Baseline visit) and on Day 14 (Visit 3). Results are collected as normal or abnormal (not clinically significant or clinically significant) only.

6.4.2.4.3 Physical and Neurological Examination

A complete physical examination will be performed at Screening/Baseline (Day 1). Physical examinations may be abbreviated (i.e. disease-specific and symptom directed) on Days 4, 14, 28.

A neurological examination will be performed at Screening/Baseline (Day 1), Day 4 and 14. Overall status (improved, stable, or deteriorated) will be collected.

6.4.2.4.4 Prior and Concomitant Medications

Concomitant use of medications, including rescue analgesia other than study-provided acetaminophen taken for acute back spasms, used during the study will be recorded as concomitant medications on the eCRF (see Section 13 of the study protocol for allowed and disallowed medications during the study) and will be analyzed at the time of report following dosing of study drug through Visit 4 (Day 28).

6.4.3 *Population Pharmacokinetics (PK)*

Blood samples for the determination of plasma tolperisone concentrations will be drawn on Day 4 (Visit 2) after completion of all study assessments for a subset of subjects.

6.5 **Data Quality Assurance**

Report summaries will be generated using validated Base SAS[®] software, version 9.4 or higher, on a PC or server-based platform. Additional validated software may be used to generate analyses, as needed.

All SAS programs that create outputs or supporting analysis datasets will be validated by a second statistical programmer or biostatistician. At a minimum, validation of programs will consist of a review of the program log, review of output or dataset format and structure, and independent confirmatory programming to verify output results or dataset content. Additionally, all outputs will undergo a review by a senior level team member before finalization.

The content of the source data will be reviewed on an ongoing basis by project statistical programmers and statisticians. Data will be checked for missing values, invalid records, and extreme outliers through defensive programming applications, analysis-based edit checks, and other programmatic testing procedures. All findings will be forwarded to the project data manager for appropriate action and resolution.

7 STATISTICAL METHODS

7.1 General Methodology

Data will be analyzed by Precision for Medicine biostatistics personnel. Statistical analyses will be reported with tables, figures, and listings, presented in rich text format, and using recommended ICH numbering. Output specifications for all tables, figures, and listings will be in conformance with guidelines specified by the ICH in Appendix 7 of the *Electronic Common Technical Document Specification* (Apr 2003).

7.1.1 Reporting Conventions

Tables and figures will be summarized by tolperisone dose group/placebo. Tables summarizing demographics, baseline characteristics and all safety endpoints will also include a column for all tolperisone treated subjects combined. In general, all data collected and any derived data will be presented in subject data listings, for all enrolled subjects. Listings will be ordered by treatment group, site, subject number, and assessment or event date. The treatment group presented in listings will be based on the planned assignment, unless otherwise noted.

In general, continuous variables will be summarized to indicate the study population sample size (N), number of subjects with available data (n), mean, SD, median, 25th (Q1) and 75th (Q3) quartiles, minimum, and maximum values. Categorical variables will be summarized by the population size (N), number of subjects with available data (n), number of subjects in each category, and the percentage of subjects in each category. Unless otherwise noted, the denominator to determine the percentage of subjects in each category will be based on the number of subjects with available data. Select ordinal data may be summarized using both descriptive statistics and counts and percentages of subjects in each category, as appropriate.

Non-zero percentages will be rounded to one decimal place. Rounding conventions for presentation of summary statistics will be based on the precision of the variable of summarization, as it is collected in its rawest form (i.e., on the electronic case report form [eCRF] or as provided within an external file) and are outlined as follows:

- The mean and median will be rounded to one more decimal place than the precision of the variable of summarization;
- Measures of variability (e.g., SD, SE) will be rounded to two more decimal places than the precision of the variable of summarization; and
- Minimum and maximum values will be presented using the same precision as the variable of summarization.

Other statistics (e.g., CIs) will be presented using the same general rules outlined above, or assessed for the most appropriate presentation based on the underlying data.

Unless otherwise specified, 95% confidence intervals will be calculated for point estimates and statistical significance testing will be two-sided and performed using $\alpha=0.05$. P-values will be reported for all statistical tests, rounded to four decimal places. P-values less than 0.0001 will be

displayed as “<0.0001”; p-values greater than 0.9999 will be displayed as “>0.9999”. Tests of interaction terms, if applicable, will be two-sided and performed using $\alpha=0.10$.

